#### 1 INTRODUCTION

The purpose of this document is to give details for the statistical analysis of study D5671C00006 Part A data supporting the clinical study report (CSR). The reader is referred to the clinical study protocol (CSP) and the case report form (CRF) for details of study conduct and data collection.

This study was originally designed as a 2-part, Phase IIb/III, global, randomized, parallel-group, double-blind, placebo-controlled, multicenter study to assess the safety and efficacy of 300 and 600 µg cotadutide compared with placebo, given once daily as a subcutaneous injection administered via a multidose pen, in adults with non-cirrhotic non-alcoholic steatohepatitis (NASH) with fibrosis stage F2 or F3. After carefully considering several factors, foremost being the identification of other, more convenient treatments for patients with NASH, the sponsor made a strategic decision to discontinue development of cotadutide and recruitment into this study. Randomized participants and participants in active screening were allowed to continue participation. Given the reduced sample size, the primary goal of this study is to evaluate the safety and tolerability of cotadutide in participants with non-cirrhotic NASH with fibrosis. The originally planned Phase III portion of the study (Part B) will not be conducted and most references to it have been removed from this document.

Part A (Phase II) will assess the safety and efficacy of 300 μg and 600 μg cotadutide treatment.

In Part A, 300 participants were originally planned to be randomized to provide > 90% power for the test of each dose versus pooled placebo to detect a difference of 20% in NASH resolution assuming a placebo response rate of 15%. As a result of the decision to terminate recruitment, approximately 55 participants are planned to be randomized in the study.

At randomization, participants in Part A will be stratified by the presence/absence of type 2 diabetes mellitus (T2DM) and by fibrosis stage.

## 2 CHANGES TO PROTOCOL PLANNED ANALYSES

In response to a quality incident (QE-341716), the per protocol set was updated to exclude participants from Site PPD due to GCP concerns. No other changes were made in the conduct of the study or in the planned analyses reported in this statistical analysis plan (SAP) with respect to the last CSP version.

## 3 DATA ANALYSIS CONSIDERATIONS

# 3.1 Timing of Analyses

After all participants in Part A of the study have completed the study and clinical data lock for Part A has occurred, Part A will be unblinded and analyzed.

# 3.2 Analysis Populations

The following analysis populations are defined in Table 1:

Table 1 Populations for Analysis

Population/Analysis set	Description
Enrolled	All participants who sign the ICF.
Randomized	All participants randomized into the study.
FAS	All participants who have been randomized to and received at least 1 dose of IP.
PP	Subset of FAS population with evaluable post-baseline biopsy after at least 36 weeks of treatment. In response to a quality incident (QE-341716), participants from Site PPD will be excluded due to GCP concerns.
Safety	The Safety analysis set consists of all participants who have received at least 1 dose of IP. Erroneously treated participants (eg, those randomized to treatment A but actually given treatment B) are accounted for in the treatment group with the majority of estimated usage. In all cases, the dose level for analysis will correspond to the randomized dose.
PK	The PK population includes all participants who receive at least 1 dose of study intervention and have at least 1 complete intended PK sample containing detectable cotadutide concentrations.

FAS, full analysis set; ICF, informed consent form; IP, investigational product; PK, pharmacokinetic(s); PP, per protocol.

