# **6.5.2** Prohibited Concomitant Medications

Participants must be instructed not to take any medications, including NASH-related over-the-counter products, without first consulting with the investigator

Use of the following medications will be restricted (Table 9) or prohibited (Table 10) as specified:

**Table 9** Restricted Medications

Medication/class of drug:	Usage (including limits for duration permitted and special situations in which it is allowed ):
Systemic corticosteroids by oral, intravenous, or intramuscular route	Not to be used within 90 days prior to baseline biopsy (historical or screening) and during the study unless prescribed for a very brief period of less than 14 days
Prokinetic agents such as domperidone and metoclopramide	Only to be used during the study for the treatment of nausea and vomiting if a centrally acting antiemetic is deemed ineffective or not tolerated by the participant
Analgesics and antipyretics	Careful use of paracetamol (acetaminophen) is allowed, not to exceed 3 g/d

**Table 10** Prohibited Medications

Prohibited medication/class of drug:	Usage
Therapies associated with development of NAFLD such as methotrexate, tamoxifen, amiodarone, or long-term use of tetracyclines or systemic corticosteroids	Within 90 days prior to baseline biopsy (historical or screening) until the end of the study. Systemic corticosteroid and tetracycline use are restricted during the study unless prescribed for a very brief period of ≤ 14 days.
Therapies in classes under investigation for the treatment of NASH (except for SGLT-2 inhibitors), such as obeticholic acid, pioglitazone, and Vitamin E	Within 180 days of baseline biopsy until the end of the study. In the case of pioglitazone or high-dose vitamin E, these drugs are restricted during the study unless the participant has been on a stable dose for at least 180 days prior to baseline biopsy (historical or on-study). Potential drugs with new regulatory approvals for the treatment of NASH with fibrosis stage F2/F3 could be considered after discussion with study physician, if the investigator deems it not to be safe for the participant to postpone the start of such treatment until study end.
GLP-1 receptor agonists and GLP-1 receptor agonist containing therapies	Within 90 days of baseline biopsy (historical or onstudy) until the end of the study

**Table 10** Prohibited Medications

Prohibited medication/class of drug:	Usage

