# 3.3.1.2 Definition of On-study and On-treatment

All adverse events (AEs) with start date on or after the date of first treatment will be considered on-study. On-treatment AEs are those occurring within the on-study period and within + 7 days of treatment discontinuation. All AEs leading to discontinuation of IP will be considered on-treatment.

On-study assessments (eg, vital signs, clinical laboratory tests, ECG) are defined as those occurring after the date and time (if available) of administration of the first dose of IP. On-

treatment assessments are defined as those occurring within the on-study period and on or before the date of administration of the last dose of IP with the following windows following treatment discontinuation:

- Fasting plasma glucose (FPG): +1 day from treatment discontinuation.
- Biopsy, liver tests (alanine aminotransferase [ALT], aspartate aminotransferase [AST], total bilirubin [TBL], and alkaline phosphatase [ALP]), and disease-specific biomarkers: + 30 days from treatment discontinuation.
- All other efficacy and safety: +7 days from treatment discontinuation.

Assessments other than AEs recorded on the day of first treatment and with time unavailable for the assessment or for the first dose, will be considered to be not in the on-study/on-treatment periods. For listings of AEs, analysis phase will be indicated as on-treatment if the AE starts within the on-treatment period, as 'pre-treatment' if it starts prior to the on-treatment period, and as 'post-treatment' if it starts after the on-treatment period.

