# 3.3.5 Handling of Protocol Deviations in Study Analysis

The list of important protocol deviations (IPDs) is provided in the Protocol Deviation Plan.

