#### Possible reasons for exclusion from analysis sets will be:

- Randomized set: Participant not randomized.
- FAS: Participant not randomized OR participant did not receive at least 1 dose of the IP.
- PP: Participant not randomized OR participant did not receive at least 1 dose of the IP OR did not have evaluable post-baseline biopsy after at least 36 weeks of treatment OR participant excluded due to site GCP concerns (Site PPD
- Safety set: Participant did not receive at least 1 dose of the IP.

• PK (pharmacokinetics) set: Participant did not receive at least 1 dose of the IP OR participant did not have at least 1 detectable cotadutide concentration.

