## 4.2.3.4 Primary Analysis of Other Endpoints

Unless otherwise indicated, analyses of tertiary/exploratory histological endpoints and continuous exploratory endpoints at Week 48 will include both on- and off-treatment measurements while analyses of endpoints at multiple timepoints through Week 48 will only include on-treatment measurements. The treatment effect for binary exploratory endpoints will be analyzed by the Cochran-Mantel-Haenszel (CMH) test, stratified for T2DM presence and F2/F3 fibrosis stages. The difference in proportion (unstratified response difference) with Miettinen-Nurminen (ie, score-based; without stratification) 95% confidence interval, and nominal p-value from CMH chi-square test will be provided.

Continuous endpoints summarized for a single post-baseline timepoint (Week 48) will be analyzed using ANCOVA with baseline, baseline T2DM status, baseline fibrosis stage, and treatment as independent variables, using multiple imputation. If an issue is encountered for fitting an ANCOVA model (eg, collinearity with intercept), a simplified model may be used. For analysis of (absolute) change from baseline, endpoints will be analyzed without transformation and LSMEAN change from baseline by treatment; the treatment effect as the LSMD will be reported as point estimates and 95% confidence intervals with p-values provided for treatment effect. For analysis of percent change from baseline, ANCOVA will be performed using log-transformed values. Point estimates and 95% confidence intervals of percent change from baseline by treatment and ratio change from baseline will be reported with a nominal p-value for treatment effect (Section 4.2.3.2). Rubin's rules (Rubin 1987) will be used to pool LSMEAN and LSMD values and associated standard errors across multiply imputed datasets and will provide the reported estimates and p-values. The following variables will be log-transformed: ALT, AST, APRI, triglycerides, PRO-C3, FIB-4, FPG, (total and high molecular weight) adiponectin, and C-peptide. Other variables may be log-transformed if required.

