## **4.5.1 Exposure**

## **4.5.1.1 Definitions and Derivations**

As per the CSP, participants start the subcutaneous injections of the study IP at day 1. Study IP is dispensed to the participant for self-administration at home.

Exposure (days) is calculated only for participants in the safety population as the total number of days on study drug (ie, gaps in dosing due to study drug interruption will not be taken-out from the calculation). Exposure is calculated as the study drug dose last date minus study drug dose first date plus 1.

Cumulative exposure (days) is also computed based on exposure, using the following duration (days) categories:

- 12 weeks (≥ 84 days)
- 24 weeks (≥ 168 days)
- 48 weeks (≥ 336 days)

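### The per protocol set keeps participants who took prohibited GLP-1, weight-loss or NASH drugs before the biopsy, or were biopsied long after stopping study drug, and no other planned histology analysis removes them

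*SAP*

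**What the plan says.** SAP Table 1 (3.2) defines PP as "Subset of FAS population with evaluable post-baseline biopsy after at least 36 weeks of treatment" and excludes one site after a quality incident. Protocol Table 14 has the same definition without the site exclusion. SAP 4.1.2.1 lists the reasons for leaving PP: not randomized, not dosed, "did not have evaluable post-baseline biopsy after at least 36 weeks of treatment OR participant excluded due to site GCP concerns". Concomitant medication, important protocol deviations and time since last dose are not on the list.

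The neighbouring rules do not fill the gap:

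- **Deviations.** SAP 3.3.5 says only that "The list of important protocol deviations (IPDs) is provided in the Protocol Deviation Plan". SAP 4.1.3.2 summarizes and lists them in the FAS.
- **Prohibited medication.** SAP 4.1.8.1 defines it and says how it is identified. SAP 4.1.8.2 tabulates it in the safety population. It does not feed PP.
- **Timing of the biopsy.** SAP 3.3.1.2 sets an on-treatment window for biopsy, liver tests "and disease-specific biomarkers: + 30 days from treatment discontinuation". SAP 4.2.3.4 says that histology analyses at Week 48 "will include both on- and off-treatment measurements", with no separate rule for PP. SAP Table 2 accepts a biopsy from Day 1 to the end of the study.
- **Other histology analyses.** SAP 4.2.3.5 plans none.

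Protocol Table 10 prohibits GLP-1 receptor agonists, weight-loss drugs and other NASH therapies until the end of the study. It also says: "Potential drugs with new regulatory approvals for the treatment of NASH with fibrosis stage F2/F3 could be considered after discussion with study physician". That route is conditional on the investigator judging it unsafe to delay such a drug until the study ends.

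**The concern.** Readers usually take a per protocol result to describe participants who took the assigned treatment without an important competing one. Here a participant can stop study drug at Week 36, start a GLP-1 receptor agonist, be biopsied at Week 48, and still be in PP. Protocol 1.1 itself says that GLP-1 mono-agonists improve the histological features of NASH.

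The FAS analysis (SAP 3.3) already takes biopsies as observed despite discontinuation or prohibited medication. PP treats discontinuation after Week 36, and prohibited medication, in the same way. The two planned analyses therefore cannot show whether a histology result depends on these participants. With about 55 randomized, one or two such participants can change the picture.

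**Working it through.** **1. The plan's own figure.** Protocol 9.2 gives power above 90% for 100 per dose against 100 pooled placebo, 15% versus 35%, two-sided 0.05. With the pooled-variance normal approximation:

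- SE under no difference = √(2 × 0.25 × 0.75 / 100) = 0.0612
- SE under the alternative = √((0.15 × 0.85 + 0.35 × 0.65) / 100) = 0.0596
- Power = Φ[(0.20 − 1.96 × 0.0612) / 0.0596] = Φ(1.34) = 91.0%

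The figure reproduces. The concern does not rest on it, but it supplies the 20-point yardstick used below.

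**2. Who is removed, by event.**

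| Event | FAS | PP |
|---|---|---|
| Stopped before 36 weeks, biopsied at Week 48 | observed result | excluded |
| No biopsy | non-responder | excluded |
| Stopped after 36 weeks, biopsied off drug | observed result | observed result |
| Prohibited GLP-1, weight-loss or NASH drug before biopsy | observed result | observed result, if treated at least 36 weeks |

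PP differs from the FAS in the first two rows (and by the excluded site), and not in the last two.

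**3. Time off drug that PP accepts.** Inputs: 36 weeks = 36 × 7 = 252 days, so last dose on Day 252; Week 48 target Day 337 (SAP Table 2); biopsy allowed until 4 weeks after Visit 11 (Protocol Table 4 footnote); visit window ± 5 days.

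- Biopsy at Day 337: 337 − 252 = 85 days
- Biopsy at Week 48 + 4 weeks: 337 + 28 − 252 = 113 days
- The same with Visit 11 five days late: 337 + 5 + 28 − 252 = 118 days
- Against the 30-day window: 85/30 = 2.8 times and 113/30 = 3.8 times

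Day 252 assumes that treatment is counted from first to last dose. The SAP does not say how PP counts its 36 weeks. Its only exposure formula (4.5.1.1) is last minus first dose date plus 1, where "gaps in dosing due to study drug interruption will not be taken-out from the calculation".

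**4. Who can exceed 30 days.** For a Day 337 biopsy, a last dose on Day 306 gives 31 days and on Day 307 gives 30. Only stops from Day 252 to Day 306 are affected. Earlier stops are already out of PP.

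**5. Weight of one participant.** 55 randomized 2:1:2:1 gives 55 × 2/6 ≈ 18 per dose and ≈ 18 in pooled placebo. The PP size is not given; assume 10 to 14 per group. One participant is then 1/14 = 7.1 to 1/10 = 10.0 points. Against a 20-point difference:

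- one extra placebo responder leaves 20 − 10.0 = 10.0 to 20 − 7.1 = 12.9 points;
- one extra cotadutide-arm responder gives 20 + 7.1 = 27.1 to 20 + 10.0 = 30.0 points.

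The shift can go either way.

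**The case against.** The best reply has five parts.

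- **PP does act on discontinuation.** Protocol 7.1 encourages early stoppers to have the Week 48 biopsy. Someone who stopped at Week 10 counts in the FAS by observed result and is out of PP. The cut-off also matches the rationale in Protocol 4.2.2 that resolution may be visible by 36 weeks. This stands. A reader might infer that PP is only the FAS without missing biopsies; the definition does not support that.
- **No document sets PP the task of estimating an effect free of other drugs.** This also stands. The stated estimand is treatment policy, and no estimand is attached to PP. PP therefore does not fail a declared aim. The point is that its label invites a reading that its definition does not deliver.
- **Excluding participants after randomization adds selection.** This stands, and the restricted result must carry that warning.
- **The exposure to the problem is narrow.** Table 10's route for a newly approved drug is conditional, and a participant using it acts within the protocol. Those unable or unwilling to wait for Week 48 are biopsied around the early discontinuation visit. The 85 to 113 days are upper figures. All of this limits how many may be affected, but gives no number.
- **The cases are partly visible.** Prohibited medication is tabulated, and deviations and exposure are listed. A reader could trace individuals, but no histology result would be shown without them. The Protocol Deviation Plan is not available here, but SAP 4.1.2.1 does not link it to PP.

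A reader might also infer that the bias runs towards no difference, because placebo participants who are not improving would start other drugs. The documents do not say who used such drugs or in which arm. A cotadutide participant who stops and switches to a GLP-1 drug could push the other way.

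**Conclusion.** The point holds in a limited form. PP removes participants treated for under 36 weeks, those without an evaluable biopsy, and one site. It keeps users of prohibited GLP-1, weight-loss or NASH drugs, and biopsies up to 85 days (Day 337) or 113 days (Week 48 + 4 weeks) after last dose, against the SAP's 30-day window. For those events it repeats the FAS handling, and no other histology analysis is planned.

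The day counts follow from the documents, given first-to-last-dose counting. The 7 to 10 points per participant rest on the assumed 10 to 14 per group. How many are affected, in which arm, and in which direction cannot be determined.

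The consequence is confined to interpretation of exploratory histology with nominal p-values. At about 18 per group, the formula above gives about 28% power for 15% versus 35%, so these results will be imprecise in any case. The primary safety objective is untouched. It is a cheap improvement worth making.

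**What to change.** Before unblinding, either add the restriction below to PP in SAP Table 1 and 4.1.2.1, or keep PP and run the restriction as a supplementary analysis under SAP 4.2.3.5. The second route leaves the definition shared with Protocol Table 14 alone; the first needs an entry in SAP Section 2.

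- **(a)** The biopsy falls in the SAP 3.3.1.2 on-treatment window, that is, no later than last dose + 30 days.
- **(b)** From first dose to biopsy there was no use of a GLP-1 receptor agonist, weight-loss drug or other NASH therapy as flagged under SAP 4.1.8.1, including a newly approved NASH drug started on study. Stable pioglitazone or vitamin E permitted by Protocol 6.5.1 stays in.

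Report the number removed by arm and reason. State that the result comes from a subset selected after randomization, is supplementary, and is not an unbiased effect estimate.

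**Cost.** SAP wording and one derivation from medication flags, last-dose dates and biopsy dates that the SAP already uses. Protocol 6.3.2 already requires evaluability decisions before codes are broken. A few participants will be lost, with some added selection. Condition (a) can also remove a completer: with a biopsy at Day 365, a last dose on Day 334 or earlier (three or more days before a Day 337 visit) gives at least 31 days. The FAS analysis does not change.

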#### 3.3 General Considerations

The primary analyses will be of safety. No formal hypothesis testing will be performed. Treatments will be compared in tables using descriptive statistics.

Exploratory efficacy analyses will use nominal 2-sided 5% significance levels (equivalent to nominal 1-sided 2.5% significance levels) unless otherwise stated.

The primary estimand of interest for the histological endpoints will use the treatment policy strategy. The treatment policy approach applies to intercurrent events of treatment discontinuation, deviations from the protocol titration schedule, changes in background medication, liver events, or use of prohibited medication or other protocol deviations.

For efficacy analyses, participants will be analyzed according to their randomized investigational product (IP) assignment and dose, irrespective of the treatment they actually received. Analyses will be performed using the full analysis set (FAS) and/or per protocol (PP) analysis sets, as appropriate. The FAS will include all randomized and treated participants who received at least 1 dose of IP irrespective of their protocol adherence, addition, or modification of background medications, discontinuation of study intervention or switches to alternative medications, and continued participation in the study.

All statistical summaries and analyses will be performed using Statistical Analysis System (SAS®) software version 9.4 or above (SAS Institute, Cary, North Carolina, USA).

# **3.3.1** General Study Level Definitions

#### 3.3.1.1 Definition of Baseline

Baseline biopsy specimen refers to either historical biopsies or on-study biopsies obtained during the screening period. Central pathology review of the eligibility read will occur upon baseline biopsy specimen receipt and processing at the histopathology vendor. Central pathology review results will support patient eligibility and enrollment. This is referred to as the eligibility read and will serve as the baseline for histology analyses.

For continuous endpoints, the baseline value for statistical analysis is the last non-missing value on or prior to date and time (if available) of administration of the first dose of IP. If multiple measurements occur on the same day, the last non-missing value on or prior to the time of first dosing of study drug will be considered as the baseline value. If these multiple measurements occur at the same time or the time is not available, the average of these measurements (for continuous data) will be considered as the baseline value. For electrocardiogram (ECG) parameters, the mean of the last set of triplicate measures prior to treatment is baseline.

For categorical endpoints, the last available record on or prior to the date of the first dose of study drug will be selected. If there are ties in terms of proximity to first dose, the value with the lowest severity will be selected (eg, normal will be selected over abnormal for safety ECG findings and '+' will be selected over '++' for urinalysis findings).

